Finally, we will also interview a small number of participants as well as people working in vaccine clinics to gain their views on our approach to improving vaccine effectiveness. This work will help to identify if there is an easy and effective way to make vaccines work better that is acceptable to doctors and patients, doesn't have any side effects and which anyone, anywhere can try.

4. Synopsis

Study title	A feasibility randomised controlled trial examining the effect of a positive mood intervention and vitamin D supplementation on the immunological responses to a boosting COVID-19 and/or influenza vaccination in healthy adults		
IRAS reference	316876		
Short title	PROTECTIVE-D: imPROving the effecTivenEss of vaccinaTion wltH positive mood and Vitamin D		
Participants	Adults aged 65 years and over eligible for COVID-19 booster vaccination in Autumn 2022		
Sample size	~40		
Treatment	Positive mood intervention +/- vitamin D supplementation		
Treatment duration	7-28 days		
Study duration	12 months		
Planned study period	November 2022 to November 2023		
Objectives	Outcome measures	Evaluation time points	
Primary	Feasibility and acceptability of study interventions for testing in future studies	Qualitative assessment of acceptability of interventions. Intervention adherence measures.	4 weeks

**University of
Nottingham**
Health Service

Exploratory	Assessment of effectiveness of study intervention in improving immune response to COVID-19 boosting and/or influenza vaccination.	Anti-SARS-CoV-2 immunoglobulin levels +/- vaccine induced influenza immunoglobulin levels	4 weeks 24 weeks
	Further investigate immunological response to intervention.	SARS-CoV-2/influenza neutralising antibodies and T-cell responses.	4 weeks

**University of
Nottingham**
Health Service

5. Abbreviations

AE:	Adverse Event
AR:	Adverse Reaction
CI:	Chief Investigator
CRF:	Case Report Form
CTIMP:	Clinical Trial of Investigational Medicinal Product
DSUR:	Development Safety Update Report
EudraCT:	European Clinical Trial Database
FDA:	Food and Drug Administration
GCP:	Good Clinical Practice
GDPR:	General Data Protection Regulation
HRA:	Health Research Authority
ICF:	Informed Consent Form
ISF:	Investigator Site File
PI:	Principal Investigator
PIS:	Participant Information Sheet
PPI:	Patient and Public Involvement
REC:	Research Ethics Committee
SAE:	Serious Adverse Reaction
SAE:	Serious Adverse Event
SOP:	Standard Operating Procedure
SUSAR:	Suspected Unexpected Serious Adverse Reaction

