UNHS:	University of Nottingham Health Service

**University of
Nottingham**
Health Service

6. Background and rationale

Vaccines play a critical role in reducing the burden of infectious disease in the population. However, with all vaccines there is variability in the effectiveness and durability of protection, with the greatest variability evident in older people. Previous research has shown that a range of emotional and lifestyle factors alter vaccine effectiveness including positive and negative mood^{1,2} and vitamin D status³ and that interventions which target these factors can enhance vaccine success⁴. Furthermore, there is evidence that vitamin D and negative mood may be inversely related, suggesting that an intervention which combines both adjuvants may have synergistic effects.

The proposed project would build on existing evidence which has demonstrated the benefits of positive mood and vitamin D for vaccine effectiveness. The aims would be to:

1. Adapt an existing brief single session positive mood intervention to permit delivery of multiple sessions in the seven days post-vaccination
2. Assess the feasibility and acceptability of vitamin D supplementation for 28 days and a brief positive mood intervention for 7 days in older adults.
3. Gather preliminary evidence on the effects of positive mood alone, vitamin D alone and positive mood and vitamin D in combination on the antibody response to influenza and SARS-CoV-2 virus vaccines
4. Investigate the cellular and humoral immune mechanisms mediating intervention effects

**University of
Nottingham**
Health Service

7. Methods

Patients aged 65 years or greater being targeted for COVID-19 and/or influenza vaccination will be recruited from primary care to participate in a feasibility trial. They will be randomly allocated on a 1:1:1:1 basis to receive:

- No intervention (Usual Care)
- Positive mood intervention on the day of vaccination and for the following 6 days and vitamin D supplementation on the day of vaccination and once daily for the following 27 days
- Positive mood intervention on the day of vaccination and for the following 6 days
- Single dose oral vitamin D supplementation on the day of vaccination and once daily for the following 27 days

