15 ml venous blood samples will be collected to detect antibodies to the vaccine antigens. These will be measured at baseline, 4 weeks and 6 months post-vaccine to assess intervention effects on peak vaccine responses and durability of protection. Participants will also receive a daily text message reminder with a link to the positive mood intervention and/or to take their vitamin D supplement, alongside an e-diary link to complete.

A sub-sample of up to 20 patients will be invited to have blood samples collected to explore potential cellular and humoral mechanisms at day 0 and day 28. This will entail an additional maximum 60ml blood sample on each occasion.

Interviews will be conducted with patients and health care professionals involved in the pilot trial to identify barriers and facilitators to implementing the intervention in routine care.

8. Participant identification

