10.4 Safety reporting procedures

SAEs and AESIs will be reported to the CI as soon as possible after being reported to a member of the team. The CI will be responsible for deciding whether the participant is able to continue the study; whether the study can continue; and whether the sponsor should be informed.

Assignments of causality will only be made in relation to the administration of Vitamin D and/or positive mood intervention during the study. Any SAEs which occur following externally administered vaccines or medicines e.g., those given as part of the patient's usual care, will be judged to be unrelated to the study vaccine and should additionally be reported through national pharmacovigilance mechanisms as applicable.

Hospitalisation (including inpatient or outpatient hospitalisation for an elective procedure) for a pre-existing (existing prior to administration of Vitamin D during the study) condition that has not worsened unexpectedly does not constitute an SAE. Emergency department attendances should not routinely be reported as SAEs unless they meet the SAE definition described above.

The procedure for reporting of Serious Adverse Events is to complete an SAE report form for all reportable SAEs. The CI or delegate will submit (in addition to the expedited reporting above) DSURs once a year throughout the clinical trial, or on request, to the Competent Authority (MHRA), Ethics Committee, HRA (where required), Host NHS Trust and Sponsor. The safety profile will be continuously assessed by the Investigators. The CI and relevant investigators (according to the study delegation record) will also review safety and SAE issues as they arise.

**University of
Nottingham**
Health Service

11. Statistics

Evaluation of the findings will be conducted by the study team using SPSS and overseen by the study statistician [name].

The main statistical analysis will be to identify a statistically significant difference in the four groups and identify any additional immune effect of vitamin D supplementation given at the time of vaccination. We will use a range of advanced techniques, such as multivariate statistical methods and advanced clustering and classification approaches to assess the independent and combined contribution of psycho-behavioural factors to immunological responses to the vaccination.

All validated measures employed will be summarised according to published guidelines.

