11.1 Sample Size Determination

We do not specify *a priori* sample size since we will be assessing recruitment, study procedures and retention in order to inform the planning of a larger trial at a future date. We will pause recruitment when we have a minimum of 10 participants in each arm (about 40 participants in total).

At that point we will perform an interim analysis of both the quantitative and qualitative data obtained and determine whether we have enough outcome measures to meet the primary objective. This decision will be taken by the study steering group which will comprise all of the investigators and the study co-ordinator. The decision will be based on whether the data obtained is sufficient to fully inform the design of the larger trial to follow, specifically whether the methodology is acceptable to participants and study staff and whether the intervention adherence measures are capturing data as intended. We have expertise in qualitative methodology in the study steering group.

If the group feel that we have sufficient data to achieve the primary objective, the study will be stopped and the exploratory outcome data will be analysed. If the group feel further data is needed, we will not analyse exploratory outcome data at this point and recruitment will resume until a minimum of 20 patients per arm have been recruited (about 80 participants in total). When data collection is complete, we will perform a final analysis of all primary and exploratory outcome data.

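### Section 11 makes a four-group significance search, naturally read as one on immune response, the main analysis, although the protocol makes feasibility primary and immune response exploratory

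*Protocol*

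**What the plan says.** Section 11 (Statistics) opens its account of the analysis with "The main statistical analysis will be to identify a statistically significant difference in the four groups". The same sentence adds a second aim, to "identify any additional immune effect of vitamin D supplementation given at the time of vaccination". The next sentence says "We will use a range of advanced techniques, such as multivariate statistical methods and advanced clustering and classification approaches" will be used to study how psycho-behavioural factors contribute to the immune response.

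The synopsis gives the primary objective as "Feasibility and acceptability of study interventions for testing in future studies". Its outcome measures are "Qualitative assessment of acceptability of interventions. Intervention adherence measures". Antibody levels, neutralising antibodies and T-cell responses are all in the exploratory rows. Section 9 repeats that the study is about the feasibility of later large-scale testing.

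Section 11.1 sets no sample size in advance, because the study is to inform a larger trial. Recruitment pauses at a "minimum of 10 participants in each arm (about 40 participants in total"). The steering group then decides, on acceptability and adherence data, whether to stop or to continue to at least 20 per arm (about 80). Section 11.1 itself refers to the immune data as exploratory.

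Aim 3 in section 6 is to "Gather preliminary evidence on the effects of positive mood alone, vitamin D alone and positive mood and vitamin D in combination". On the antibody samples, section 7 says: "These will be measured at baseline, 4 weeks and 6 months post-vaccine to assess intervention effects on peak vaccine responses".

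**The concern.** A protocol should name as its main analysis the one that answers its primary objective. Here the analysis called main serves an exploratory objective, and section 11 says nothing about how the adherence measures, the quantitative part of the primary outcome, will be analysed. An SAP that follows section 11 conflicts with the synopsis and section 11.1, and one that follows those conflicts with section 11.

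The choice matters because the aim is stated as finding statistical significance, in a study deliberately not sized for it. If that becomes the headline, a non-significant result could be read as evidence that a component does not work. A significant result could be carried into the planning of the larger trial at an inflated size.

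**Working it through.** **What the protocol supplies.** Four arms allocated 1:1:1:1 (section 9.3); at least 10 per arm, about 40, at the pause, or at least 20 per arm, about 80, if recruitment resumes (section 11.1); withdrawals not replaced (section 9.8); no imputation (section 11.2). The totals agree: 4 × 10 = 40 and 4 × 20 = 80. There is no power figure to reproduce, because the protocol states no alpha, effect size, standard deviation (SD) or test.

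**What is assumed here.** An overall one-way F-test, alpha 0.05, Cohen's f from 0.10 to 0.40 (0.25 is the conventional medium value), and two-sided 5% for single contrasts.

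**Overall four-group test.** Power = P(F′ > F crit), where F′ is noncentral F with 3 and N − 4 degrees of freedom and noncentrality λ = N f². At N = 40 and f = 0.25, λ = 40 × 0.0625 = 2.5, the critical value is F(0.95; 3, 36) = 2.87, and power is 0.212.

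| N | f = 0.10 | f = 0.25 | f = 0.40 | f needed for 80% power |
|---|---|---|---|---|
| 36 (assumed 10% loss from 40) | 7% | 19% | 45% | – |
| 40 | 7% | 21% | 50% | 0.55 |
| 80 | 10% | 42% | 85% | 0.38 |

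For 80% power at f = 0.25, 45 per arm (180 in all) would be needed.

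**Single contrasts at 10 per arm**, in units of the outcome SD:

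- One arm against another: standard error √(2/10) = 0.447; with t(0.975; 18) = 2.101 the 95% confidence interval half-width is 0.94. A true difference of 1.33 is needed for 80% power.
- 2×2 main effect (20 against 20): standard error √(4/10)/2 = 0.316; with t(0.975; 36) = 2.028 the half-width is 0.64. A difference of 0.91 is needed for 80% power. At a true 0.5, power is 34% (60% at N = 80).
- 2×2 interaction: standard error √(4/10) = 0.632. A value of 1.82 is needed for 80% power.
- Main effect adjusted for baseline log titre, correlation r assumed: half-width 0.641 × √(1 − r²), which is 0.56 at r = 0.5 and 0.46 at r = 0.7.

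**Exaggeration.** In simulations of a true pairwise difference of 0.5 SD with 10 per arm, about 18% of comparisons were significant. The estimates in those averaged about 1.1 SD, roughly twice the truth.

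These figures let every randomised participant contribute, except in the N = 36 row. Participants may be eligible for COVID-19 vaccine, influenza vaccine or both (section 8.2), so the number for one antigen may be smaller. The protocol does not say by how much.

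**The case against.** The strongest reply is that section 11 is loosely worded rather than wrong in substance. It names no F-test, alpha or model, so every power figure above rests on assumptions. Section 11.1 promises a final analysis of primary as well as exploratory data, and its stop-or-continue decision uses acceptability and adherence with no significance criterion. Ten per arm is only the minimum at a pause. A feasibility study needs no power calculation, and the protocol explains why it has none. All of this stands. It limits the point to the conflict over the main analysis and requires power to be shown as a range; it does not remove the conflict.

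Some stronger readings are tempting and are not supported:

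- *The analysis ignores the 2×2 layout.* Section 11 speaks of independent and combined contributions, and the vitamin D aim could be a main effect. The text does not exclude a factorial model.
- *The baseline sample goes unused.* Section 7 measures antibodies at baseline, and nothing says they will be left out. Covariates commonly belong in the SAP, which is not at hand.
- *A null result is nearly guaranteed.* At N = 40 it is about 79% likely at f = 0.25 but only 50% at f = 0.40, and at N = 80 power reaches 85% at f = 0.40.
- *The factorial main effects are simply the better answer.* Aim 3 asks about each intervention alone and in combination, and section 6 raises possible synergy. With synergy, a main effect averages over the other factor and is not the effect of that intervention alone.
- *Clustering and classification must be removed, and further covariates added.* That is preference, as these methods serve immune outcomes that the synopsis labels exploratory.

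The words on a difference in the four groups name no outcome. Immune response is inferred from the rest of the sentence and paragraph, which is the natural reading.

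**Conclusion.** The point holds as a contradiction in current text. Section 11 fixes as main an analysis that belongs to the exploratory objective and frames it as a search for significance; the synopsis and sections 9 and 11.1 fix feasibility, acceptability and adherence as primary. This is a stated rule in conflict with the trial's own objective, not detail left to an SAP.

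Its size depends on the assumed overall F-test and alpha 0.05. At the medium effect, power is 21% with 10 per arm and 42% with 20 per arm, and only the largest effect considered, at 20 per arm, passes 80%. Over most of that range a non-significant result would therefore be uninformative, and a significant one would tend to overstate the effect. The absence of a power calculation is not itself a fault. The section should be corrected before any data are analysed.

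**What to change.** Rewrite the opening of section 11 along these lines:

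- The main analysis estimates adherence and the other quantitative feasibility outcomes with 95% confidence intervals, alongside the qualitative analysis of acceptability.
- Antibody outcomes are exploratory. They are reported separately for each antigen as estimates with 95% confidence intervals, adjusted for the baseline log titre already collected, and not interpreted by statistical significance.
- Each intervention arm is compared with usual care, which gives the effects that aim 3 asks for. The 2×2 main effects and interaction are reported as well, with a note that the main effects equal the effects of each intervention alone only if there is no interaction.
- Any clustering or classification is labelled hypothesis-generating.

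The SAP, if there is one, should carry the same hierarchy. No new data or visits are needed. The cost is an amendment to the wording and the loss of a headline p-value. Intervals will still be wide (half-widths at N = 40, unadjusted, of 0.94 SD for an arm against usual care and 0.64 SD for a main effect), but they show openly what the study can and cannot tell the larger trial.

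### Section 11 makes a significance search on an exploratory immune outcome the main analysis of a feasibility trial that was not sized for it

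*Protocol*

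**What the plan says.** The synopsis (section 4) gives the primary objective as "Feasibility and acceptability of study interventions for testing in future studies", with these measures: "Qualitative assessment of acceptability of interventions. Intervention adherence measures". The row labelled exploratory reads "Assessment of effectiveness of study intervention in improving immune response to COVID-19 boosting and/or influenza vaccination". Section 6 pitches the antibody aim at the same modest level: "Gather preliminary evidence on the effects of positive mood alone, vitamin D alone and positive mood and vitamin D in combination".

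Section 11.1 specifies no a priori "sample size since we will be assessing recruitment, study procedures and retention in order to inform the planning of a larger trial". The investigators will "pause recruitment when we have a minimum of 10 participants in each arm (about 40 participants in total"), then either stop or go on to at least 20 per arm, about 80 in total. That choice depends on whether the data meet the primary objective.

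Section 11 nevertheless says: "The main statistical analysis will be to identify a statistically significant difference in the four groups", and adds that the analysis will "identify any additional immune effect of vitamin D supplementation given at the time of vaccination". The first clause names no outcome. The second clause does, and the next sentence of section 11 again concerns immunological responses, so reading the main analysis as a test of the immune outcome is fair.

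**The concern.** The label of main analysis sits on an outcome that the synopsis calls exploratory, and the stated goal is to find significance. This is a rule written in the protocol, not a detail left to a statistical analysis plan. A plan that follows section 11 inherits the conflict, and a plan that follows the synopsis departs from section 11.

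Two things are at stake. First, the result presented as the main one would not answer the trial's own question, whether the interventions are feasible and acceptable enough to take into a larger trial. Second, with 10 or 20 per arm a significance verdict says little about small to moderate effects: failing to reach significance is the likely outcome whether or not the interventions work, and reaching it selects for overestimates.

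**Working it through.** **The plan's own figures.** 4 arms × 10 = 40 and 4 × 20 = 80, as section 11.1 says. It states no power, so there is no power figure to reproduce.

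**Inputs.** From the protocol: four arms, 1:1:1:1, n = 10 or 20 per arm. Assumed, because the protocol is silent: two-sided alpha 0.05, SD 1, no dropout, standardised difference d. Withdrawals are not replaced (section 9.8) and missing values are not imputed (section 11.2), so dropout from these numbers would lower power.

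**Pairwise comparison of two arms.** Noncentral t with noncentrality d × √(n/2) and 2n − 2 degrees of freedom.
- n = 10, d = 0.5: 0.5 × √5 = 1.118, 18 df, critical value 2.101; power 18.5%.
- n = 20, d = 0.5: 0.5 × √10 = 1.581, 38 df, critical value 2.024; power 34%.

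**2x2 main effect.** The arms are neither, both, mood alone and vitamin D alone, so each component can be tested on pooled margins (no interaction assumed): 20 v 20 at N = 40 and 40 v 40 at N = 80.
- N = 40, d = 0.5: noncentrality 0.5 × √10 = 1.581; power 34%.
- N = 80, d = 0.5: noncentrality 0.5 × √20 = 2.236; power 60%.

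**Four-group F test.** Noncentrality N × f². At f = 0.25 this is 40 × 0.0625 = 2.5 and 80 × 0.0625 = 5; power 21% and 42%.

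| Power | N = 40 | N = 80 |
|---|---|---|
| Pairwise, d = 0.3 | 10% | 15% |
| Pairwise, d = 0.5 | 19% | 34% |
| Pairwise, d = 0.8 | 40% | 69% |
| Main effect, d = 0.3 | 15% | 26% |
| Main effect, d = 0.5 | 34% | 60% |
| Main effect, d = 0.8 | 69% | 94% |
| Four-group, f = 0.25 | 21% | 42% |

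Pairwise power of 80% needs d = 1.32 with 10 per arm and 0.91 with 20. Conversely, d = 0.5 needs 2 × (1.960 + 0.842)² / 0.5² ≈ 63 per arm.

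**Precision.** The half-width of a pairwise 95% confidence interval is t × √(2/n): 2.101 × √0.2 = 0.94 SD with 10 per arm and 2.024 × √0.1 = 0.64 SD with 20.

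**Exaggeration among significant results.** With 10 per arm and an observed SD of 1, a difference must reach 0.94 SD to be significant, already 0.94 / 0.5 = 1.88 times a true d of 0.5. By simulation (400,000 replicates), the mean absolute difference given p < 0.05, divided by the true d, is:

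| True d | Pairwise, 10/arm | Pairwise, 20/arm |
|---|---|---|
| 0.3 | 3.5 | 2.6 |
| 0.5 | 2.2 | 1.7 |
| 0.8 | 1.5 | 1.2 |

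For a main effect at d = 0.5 the ratio is 1.7 at N = 40 and 1.3 at N = 80.

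**What estimating the primary outcome would give.** At N = 40 each component is assigned to 20 people. If 16 of 20 adhered (an illustrative 80%), the Wilson interval has centre (0.8 + 3.8415/40) / (1 + 3.8415/20) = 0.752 and half-width 1.96 × √(0.8 × 0.2/20 + 3.8415/1600) / 1.192 = 0.168, so 58% to 92%. At N = 80, 32 of 40 gives 65% to 90%.

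**The case against.** The strongest reply has four parts.

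*The primary objective is provided for elsewhere.* A reader of section 11 might infer that it has no analysis at all. The protocol does not support that. Section 9.4 plans thematic analysis of the interviews, section 9.7 defines a compliance proportion, and section 11.1 sets an interim review against the primary objective and promises a final analysis of the primary outcomes. The detailed method for adherence may be in a statistical analysis plan not seen here, so its absence is not an error. What stands is that none of this is what section 11 calls the main analysis. Nor does the compliance definition fill the place, since it counts the diary, a vaccine dose and blood samples, not vitamin D doses or mood sessions.

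*The test need not be weak.* A reader might infer that no significance test at this size could be useful, or that non-significance is nearly certain. Neither follows. A main effect of d = 0.8 has 94% power at N = 80, with exaggeration of only about 1.04-fold. Adjusting for the baseline sample would help: with an assumed baseline correlation of 0.5 to 0.7, main-effect power at d = 0.5 rises to roughly 43–58% at N = 40 and 72–87% at N = 80. But section 11 commits to neither approach, and speaks of a difference among the four groups.

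*The larger trial may not be sized on the observed effect.* That would be a natural fear given the exaggeration, but no section says it will happen. Section 11.1 names acceptability and the capture of adherence data as what informs the next design.

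*There are safeguards.* The decision to stop or continue does not depend on immune significance, and exploratory outcomes are left unanalysed if recruitment resumes. This limits the harm but does not remove the conflict over which analysis is the main one.

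**Conclusion.** The conflict is real and can be seen in the protocol alone: section 11 gives main status to a significance search on an outcome that the synopsis makes exploratory, in a trial for which section 11.1 sets no a priori sample size. The stated main analysis does not address the primary objective.

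The size of the problem rests on assumed inputs (two-sided 5%, SD 1, no dropout). At d = 0.5, non-significance has a probability of about 81% or 66% for a pairwise test (10 or 20 per arm) and 66% or 40% for a 2x2 main effect (N = 40 or 80). So for small to moderate effects a null result is likely in most of these settings and uninformative, and a significant pairwise result at 10 per arm is inflated about 2.2-fold on average. For large effects, with the factorial contrast and 80 participants, the test would perform well.

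This should be fixed, but it is not a critical fault. It does not affect conduct, safety or the interim decision. Confidence is high on the conflict between sections and moderate on its size, because the protocol gives no effect size or SD.

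**What to change.** Reword section 11 as follows.

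1. The main analysis is of the primary outcomes: adherence to each intervention, with recruitment and retention, each as a proportion with a 95% confidence interval, reported alongside the thematic analysis of the interviews.
2. Immune outcomes are exploratory. They are reported as between-group differences or geometric mean ratios with 95% confidence intervals.
3. Any p-values for immune outcomes are labelled exploratory and carry no conclusion of effect or of no effect.

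This changes protocol text only; it adds no participants, visits or samples. The cost is giving up a headline p-value. The change should be made before the exploratory data are analysed.
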